## 7.4 PD Endpoints

Following are the study PD endpoints.

If more than one value is obtained per-patient, per-test or per-time point, the average will be calculated.

- Eosinophil Absolute Count (serum), by visit; and change in Eosinophil Absolute
   Count compared to Baseline
- Hematoxylin and Eosin (from biopsy tissue); and change in Hematoxylin and Eosin compared to Screening
- Eotaxin-1 (serum concentration); and change in serum Eotaxin-1 level at each scheduled timepoint compared to Baseline
- BP 180 autoantibody (serum concentration); and change in BP 180 autoantibody compared to Baseline
- BP 230 autoantibody (serum concentration); and change in BP 230 autoantibody compared to Baseline
- Eosinophil Cationic Protein (ECP) (serum concentration); and change in ECP compared to Baseline

IgE (serum concentration); and change in IgE compared to Baseline
 It should be noted that ECP and IgE data were collected from samples already available and the decision to test for these markers was made after the study was completed, so the protocol was not updated to include them.

### 7.5 Exploratory Endpoints

- Peripheral Blood Mononuclear Cell (PBMC) biomarkers
- Change in PBMC biomarkers at Visit 5 compared to Visit 2 (Day 0)

### 8 Data Derivation and Transformation

Data not originally part of CRF will be derived as follows:

- Subjects age [years] = [Date of Informed Consent Date of Birth] / 365.25
- Study Duration [days]= Date of Last Visit Date of First Visit + 1.
- BMI = Weight (kg) / Height (m) $^2$
- Temperature  $[C^{\circ}] = (Temperature [F^{\circ}] 32) \times 5/9$
- Weight (kg) = Weight (lb)\* 0.45359237

## 9 Statistical Analysis

Numerical variables will be tabulated using mean, standard deviation, minimum, median, maximum and number of observations. Categorical variables will be tabulated using number of observations and percentages.

## 9.1 Subject Disposition

The following will be provided:

- Number and percent of subjects in each of the analysis populations (Safety, PK, Efficacy) by center and overall.
- Listing of subjects excluded from each of the analysis populations along with reason for exclusion.
- Consort flow diagram

- Number and percent of subjects who meet all inclusion / exclusion criteria at Visit 2
- Number and percent of subjects who were found eligible (approved by medical monitor) to participate in the study.
   For non-eligible subjects, by-subject listing, including site reason for noneligibility.

### **Study Termination:**

• Number and percent of subjects who completed the study.

Note, a subject is considered as early terminated the study if the CRF item "Indicate if the subject completed the trial or the primary reason for premature discontinuation" is not marked as "1" (Subject completed the trial).

- Frequency of premature termination reasons
- Listing of all dropouts along with the reason for termination and the time between termination and signing the informed consent form.

### **Protocol Deviations**

• Listing of protocol deviations including subject ID, date of deviation, visit/CRF term and protocol deviation.

### 9.2 Baseline Characteristics

Baseline characteristics will be analyzed using the safety analysis population. The following will be provided:

- Descriptive statistics of demographic characteristics (Age, Weight, Height, BMI, Gender, Race, Ethnicity)
- Frequency distribution of Karnofsky performance status
- Number and percent of patients who have any relevant medical history.
- By-subject listing of medical history including Subject ID, Center, Diagnosis/Symptoms, Start Date, End Date, whether Ongoing.

### **Tuberculosis Screen**

• Number and percent of patients' current TB status: Active, Inactive- No evidence of active TB, Inactive- Latent.

- For patients with latent TB, number and percent of patients who were adequately treated or controlled.
- For patients with latent TB, number and percent of patients in the risk for reactivation.
- By-subject listing of assessments performed to confirm TB status, with the corresponding results.

### **Pregnancy Test**

Frequency distribution of serum pregnancy test results.

### **Serology Test at Screening**

Results will be divided into the following categories based on the normal ranges provided by the sites:

- ✓ Clinically significant below the normal range (CS below)
- ✓ Non-clinically significant below the normal range (NCS below)
- ✓ Within the normal range (Normal)
- ✓ Non-clinically significant above the normal range (NCS above)
- ✓ Clinically significant above the normal range (CS above)

Note: The above is relevant for all tests where the normal ranges are applicable.

Frequency distribution of Serology evaluation will be presented using the above categories.

### DIF on Salt Split Skin at Screening (provided by Sponsor externally to the CRF)

The following DIF parameters will be provided externally to the CRF by the Sponsor (based on narrative reports) and presented in listing form: Immunoglobulin type (IgG, IgA, IgM, IgE – could be more than one), C3 deposition (yes/no), staining pattern (linear, granular, lace-like), site of staining (intercellular, basement membrane zone), extent of staining (diffuse vs focal), diagnosis (consistent with BP or not), unusual findings or notes. All data may not be available for all patients.

### **IIF Data at Screening (provided by Sponsor externally to the CRF)**

The following IIF parameters from subjects' screening blood samples will be provided externally to the CRF by the Sponsor and presented in listing form: Dermal IgG Ab; Anti-Dermal Abs Area; Salt split skin IIF; BP230 Ab; BP180 Ab; Desmoglein 1 Ab; Desmoglein 3 Ab.

### 9.3 Safety

All safety analyses will be performed on the safety analysis population.

### 9.3.1 Main Safety Analysis

### **Treatment Related AEs**

- Adverse Events that are possibly or probably related to treatment (including serious) will be tabulated using frequency tables with - Number of Subjects and Percentage of Subjects by:
  - Overall by System Organ Class (SOC) and Preferred Term
  - Maximal Severity by System Organ Class (SOC) and Preferred Term
  - By subject listing of treatment related Adverse Events

### **Serious Adverse Events (SAEs):**

All SAEs will be tabulated using frequency tables with - Number of Subjects and Percentage of Subjects by:

- Overall by System Organ Class (SOC), Preferred Term and maximal severity
- Overall by System Organ Class (SOC), Preferred Term and maximal relation to study drug
- By subject listing of SAEs

### **Infusion Reaction Assessment (including injection site reactions)**

 By subject listing of any infusion reactions (all responses except "no reaction"), including visit and time point.

### 9.3.2 Additional Safety Analysis

The following will be provided:

### **Adverse Events (AEs):**

All Adverse Events (including serious) will be tabulated using Frequency tables with -Number of Incidents, Number of Subjects and Percentage of Subjects by:

- Overall by System Organ Class (SOC) and Preferred Term
- Severity by System Organ Class (SOC) and Preferred Term
- Relation to study drug by System Organ Class (SOC) and Preferred Term
- Severity and Relation to study drug

• By subject listing of Adverse Events

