5.3.1 Adverse Events (AEs)

Adverse events will be assessed by the investigator throughout the study. Any AE that occurs after the informed consent is signed by the patient will be recorded in the patients' medical files as well as on the appropriate CRF page. (See Section 5.3.4).

AEs should be checked at each visit and recorded. Patients should be instructed to report any new AE that occurs between scheduled visits.

AEs will be coded by Data Management using Medical Dictionary for Regulatory Activities (MedDRA®) version 17.0 or higher.

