- d Vital signs will be measured pre-dose (any time prior to the initiation of treatment infusion), immediately at the completion of treatment infusion (approximately 30 minutes after initiation) and approximately 2 hours following initiation of treatment infusion.
- e Clinical laboratory assessments will be performed by a local laboratory for the screening visit and a central laboratory for every subsequent visit.
- f Biochemistry will include serum  $\beta$ -hCG at screening for females of childbearing potential only.
- g The patient should be evaluated for active/latent TB as applicable (e.g., PPD, QFT, and/or chest x-ray)
- h The Visit 5 (Day 42) punch biopsies should be taken in the area of the previous biopsies, as much as possible.
- i Females of childbearing potential only.
- j IIF only at screening
- k Blood samples for bertilimumab (PK analysis) will be collected pre-dose and at the completion of treatment infusion (approximately 30 minutes after the initiation) and 2 or 4 hours following the initiation of treatment infusion. PK samples 30 minutes post-infusion should be taken as close to this time as possible.
- l Semen analysis will be performed for males pre-dose and close to the completion of infusion as possible. Pre-dosing samples can be taken up to 2 days prior to dosing. m Only for males with abnormal semen analysis results from Day 0, Day 14 or Day 28 compared to pre-dose at Visit 2 (Day 0). It should be noted that in practice semen samples were not collected.
- n Adverse events and concomitant medication information to be recorded pre-dose and 2 hours after the initiation of infusion.
- o Infusion reactions should be assessed at the completion of infusion (approximately 30 minutes after the initiation) and 2 hours following the initiation of treatment infusion

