## 6 Analysis Populations

### **6.1 Safety Analysis Population**

The Safety analysis population will consist of all patients enrolled in the trial who received at least one infusion of bertilimumab 10 mg/kg.

Specifically, at least one CRF item "Date of Drug Administration" is completed.

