#### Handling of missing data:

Missing data will not be imputed, i.e. only observed data will be used.

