### 7.1.2 Additional Safety Endpoints

- Treatment emergent AEs (occurring at or after the treatment initiation)
- Physical examination
- Vital signs (blood pressure, heart rate, temperature)
- ECG
- Concomitant medications
- Laboratory evaluation:
  - Hematology
  - Biochemistry
  - Anti-bertilimumab antibodies

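### SAP 7.1.2 names treatment-emergent AEs as an endpoint, but the AE tables in SAP 9.3.2 set no onset limit, so pre-dose events of treated patients can be counted in them

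*SAP*

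**What the plan says.** SAP 7.1.2 (Additional Safety Endpoints) lists "Treatment emergent AEs (occurring at or after the treatment initiation". SAP 9.3.2 (Adverse Events) then states: "All Adverse Events (including serious) will be tabulated using Frequency tables". The columns are given as "Number of Incidents, Number of Subjects and Percentage of Subjects by" SOC and preferred term, severity, and relation to study drug, with a by-subject listing. The term treatment emergent does not appear in 9.3.2.

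Three other places determine which events reach those tables:

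- Protocol 5.3.1 starts collection at consent: "Any AE that occurs after the informed consent is signed by the patient will be recorded". Protocol 5.1 puts screening at Day -28 to Day -1.
- SAP 6.1 defines the Safety population as "all patients enrolled in the trial who received at least one infusion" of bertilimumab, and SAP 9.3 runs all safety analyses on it.
- SAP Section 8 opens with "Data not originally part of CRF will be derived as follows" and lists five derivations: age, study duration, BMI, temperature and weight. None concerns AE onset.

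**The concern.** The endpoint has an onset limit and its apparent analysis does not. A programmer who follows 9.3.2 to the letter produces all-AE tables that include screening-period events, and never produces the treatment-emergent incidence that 7.1.2 names.

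Safety is the primary objective and the trial has one arm, so no comparator shows the background level of events. A reader of the study report would naturally take the percentages in these tables as AE incidence under bertilimumab. With at most 15 patients, one misplaced patient is visible in a percentage.

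**Working it through.** **Step 1: can a pre-dose AE of a treated patient reach the 9.3.2 tables?**

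| Possible barrier | Source | Effect |
|---|---|---|
| Start of recording | Protocol 5.3.1, 5.1 | None: recording starts at consent, up to 28 days before Day 0 |
| Safety population | SAP 6.1, 9.3 | Removes screen failures; does not remove events of treated patients by date |
| Derived flag | SAP Section 8 | None defined |
| Onset limit in the table text | SAP 9.3.2 | None stated |
| Phase split | Protocol 8.0 | Calls for summaries by treatment phase and follow-up; not carried into the AE tables of SAP 9.3.2 |

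Nothing stops such an event. By contrast, the hematology and chemistry text in SAP 9.3.2 expressly leaves out screening data. The AE text does not.

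**Step 2: which events remain in the pre-dose pool?** Several rules shrink it:

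- Exclusions 4, 5 and 7 (protocol 4.2) keep out patients with clinically significant vital signs or ECG findings, clinically significant screening laboratory results, or clinically significant infection within a month of the first dose. Absent an eligibility deviation, they are never treated.
- Significant physical findings present before study drug go to medical history (protocol 5.3.5).
- Stable chronic conditions are not AEs, nor are disease-related events unless they go beyond expected progression (protocol 7.1).

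What is left is mostly minor intercurrent events. The documents give no rate for them.

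**Step 3: where would they be counted?** Under the protocol 7.1 relationship scale, possible and probable require a plausible time sequence after administration. A pre-dose event therefore belongs mainly under unrelated or unlikely.

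**Step 4: size per patient.** For one row, let T be the patients with at least one treatment-emergent event in it, P the patients whose only event in it is pre-dose, and N the Safety population.

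- Percentage as written = (T + P)/N
- Treatment-emergent percentage = T/N
- Difference = P/N

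| N | P = 1 | P = 2 | P = 3 |
|---|---|---|---|
| 15 (maximum, protocol synopsis) | 1/15 = 6.7 points | 2/15 = 13.3 points | 3/15 = 20.0 points |
| 10 (assumed) | 1/10 = 10.0 points | 2/10 = 20.0 points | 3/10 = 30.0 points |

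A patient who also has a post-dose event in the same row does not change that row's percentage. Every pre-dose event still adds 1 to the number of incidents.

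**Step 5: would applying 7.1.2 by habit be enough?** Not fully. On dosing days, "Adverse events and concomitant medication information to be recorded pre-dose and 2 hours after the initiation of infusion", so a Day 0 date alone does not show on which side of the first infusion an event began. The general rule in SAP Section 6 is "Missing data will not be imputed, i.e. only observed data will be used". SAP 7.2.1 and 7.2.2 add specific rules for blank damage scores and missing itch sub-scores. None of these covers a partial AE onset date.

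**The case against.** The best counter-argument is about the word all. SAP 9.3.1 tabulates related AEs only and 9.3.2 follows with all AEs, so all may mean all causalities, with the onset limit carried over from the endpoint definitions in Section 7. That reading is possible. But no text applies the 7.1.2 limit to 9.3.2, and the reading leaves the Day 0 and partial-date cases open.

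A second argument is that an all-AE table agrees with the protocol, whose primary endpoint is simply adverse events and whose Section 8.0 summarises all CRF data. This stands as a constraint on the remedy: pre-infusion AEs must still be reported somewhere. It does not supply the treatment-emergent analysis that the SAP names.

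A third argument is that the effect is small. This largely stands. The AE form records dates, times and pre-study presence (protocol 7.1), a by-subject AE listing is planned, and the protocol synopsis plans patient narratives, so a careful reader could find pre-dose events.

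A reader might go further and infer that the SAE table in 9.3.1 has the same error. The documents do not support that: SAP 7.1.1 lists SAEs without an onset limit, and the table matches it.

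**Conclusion.** The mismatch is real and should be corrected. As written, SAP 9.3.2 does not report the endpoint in SAP 7.1.2, and it lets pre-dose AEs of treated patients into the all-causality counts and percentages. This rests on a literal reading of 9.3.2 and on taking it, from its heading and position, as the analysis of that endpoint.

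The size is 6.7 points per affected patient per row at 15 patients; no expected total can be given. A reader might note that a full screening period is 28 of the 112 days from Day -28 to Day 84 (28/112 = 25.0%) and infer that a quarter of tabulated events are pre-dose. That does not follow. It is a share of calendar time, and the exclusions and recording rules reduce screening events by an unknown amount.

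Nor do the documents support the inference that the main safety results are distorted. Of the three main endpoints in SAP 7.1.1, related AEs need a time link to administration, infusion reactions are assessed only after an infusion, and SAEs match their own definition. No test or decision rule uses the affected figures. The consequence is confined to descriptive all-causality AE incidence.

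**What to change.** 1. In SAP Section 8, derive a treatment-emergent flag: AE onset date and time at or after the start of the first infusion. A later worsening that the site records as an AE with its own onset is handled by the same flag, in line with protocol 7.1.
2. State a rule for partial onset dates and for Day 0 onsets without a time. For example: treatment-emergent unless the available date parts or the Visit 2 pre-dose AE record show earlier onset.
3. Use the flag for the incidence, severity and relation tables in SAP 9.3.2.
4. Report pre-infusion AEs separately, in a table or listing, so that all recorded AEs are still summarised as protocol 8.0 requires.

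Showing treatment-emergent SAEs apart from earlier ones is an optional addition and is not needed to remove the mismatch.

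The cost is some wording in SAP Sections 8 and 9.3.2, one date/time filter and one extra output. The AE form already captures onset dates and times. SAP 6.1 names a CRF item for the date of drug administration but none for infusion start time; the Day 0 rule covers that gap. The downside is a small amount of extra programming.

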### **Physical Examination**

- Frequency distribution of evaluation (normal/abnormal non-clinically significant (NCS)/abnormal clinically significant (CS)/not done) by body system and visit.
- By-subject listings of CS abnormal physical examination results, including patient ID, Center, Visit, Body System and Abnormality Description.
- Shift table of normal/abnormal non-clinically significant (NCS)/abnormal clinically significant (CS) transitions from Screening to Visit 4 (last infusion) and Visit 8 (last planned FU).

### **Body Measurements**

• Descriptive statistics of Weight (kg), Height (m), BMI (kg/m²), by visit Note: Height is presented only at Screening.

#### Vital Signs

- Descriptive statistics of blood pressure (systolic / diastolic), pulse and temperature by visit and by time point
- For each treatment visit, visits 2, 3 and 4, descriptive statistics of change from pre-dose to 30 minutes, 2 and/or 4 hours post-dose will be provided
- For visits 5, 6, 7 and 8, descriptive statistics of change from baseline pre-dose (visit 2) to each subsequent visit measure will be provided.

### **ECG**

- Descriptive statistics of ECG parameters (heart rate, RR, PR, QRS, QT, QTc)
   by visit and by time point
- Frequency distribution of overall evaluation of ECG (normal/abnormal nonclinically significant (NCS)/abnormal clinically significant (CS)/not done)
- Descriptive statistics of change from Screening to last available visit
- By-subject listings of CS abnormal ECG results, including patient ID, center, visit, heart rate, RR, PR, QRS, QT, QTc, and abnormality description.

### **Anti-bertilimumab**

- Descriptive statistics of anti-bertilimumab antibodies by visit
- Change from Baseline pre-dosing (at Visit 2) to each subsequent visit

### **Hematology / Chemistry**

All hematology and chemistry tests will be divided into the following categories based on the normal ranges provided by the sites:

- ✓ Clinically significant below the normal range (CS below)
- ✓ Non-clinically significant below the normal range (NCS below)
- ✓ Within the normal range (Normal)
- ✓ Non-clinically significant above the normal range (NCS above)
- ✓ Clinically significant above the normal range (CS above)

  Note: The above is relevant for all tests where the normal ranges are applicable.
- By-test and by-subject listing of Hematology/ Chemistry results across visits.
   Note: The results will be presented using the above categories, where CS results will be highlighted. Screening data will not be presented as it was collected by separate local labs for screening purposes only and is, thus, not comparable to other rest results analyzed centrally (at one US and one Israeli central lab).
- By-subject listing of clinically significant abnormal hematology / urinalysis results.

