2.2 STUDY ENDPOINTS AND OUTCOMES

Primary Endpoints

Safety Endpoints

Safety will be evaluated on the basis of the following parameters:

- Adverse events (AE)
- Infusion reactions
- Injection site reactions
- Physical examination
- Vital signs (blood pressure, heart rate, temperature)
- ECG
- Concomitant medications
- Laboratory evaluation (hematology, biochemistry, anti-bertilimumab antibodies)

Secondary Endpoints

Efficacy Endpoints

- Proportion of patients who achieve a reduction in the Total Activity Score of the BPDAI score of at least 50%, 75% and 90% at visits 5 (Day 42), 6 (Day 56), 7 (Day 70), or 8 (Day 84) compared to:
 - Screening, if patient is resistant to corticosteroid tapering
 - Visit 2 (Day 0), if patient is newly diagnosed.
- Proportion of patients who have tapered to prednisone dose of ≤10 mg/day at Visit 8 (Day 84) and/or 2 and 4 months after Visit 8 (Day 84)
- Proportion of patients who achieve control of disease activity at Visits 5 (Day 42), 6 (Day 56), 7 (Day 70), or 8 (Day 84)
 - Ocurrol of disease activity is defined as the time when at least two of the following occur: new lesions cease to form, established lesions begin to heal and/or pruritic symptoms start to abate. Control of disease activity will be assessed by the BPDAI and the investigator's assessment of lesion healing.
- Mean time to control of disease activity from:
 - Screening, if patient is resistant to corticosteroid tapering
 - Visit 2 (Day 0), if patient is newly diagnosed
- Change in BPDAI score at each scheduled measurement timepoint compared to:
 - Screening, if patient is resistant to corticosteroid tapering
 - Visit 2 (Day 0), if patient is newly diagnosed
- Change in BPDAI pruritis component (Visual Analogue Scale) at each scheduled measurement timepoint compared to:

- Screening, if patient is resistant to corticosteroid tapering
- Visit 2 (Day 0), if patient is newly diagnosed
- Change in ABQOL score at each scheduled measurement timepoint compared to:
 - Screening, if patient is resistant to corticosteroid tapering
 - Visit 2 (Day 0), if patient is newly diagnosed

Pharmacokinetic (PK) Endpoints

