5.6.2 Eosinophil count in Blood

Eosinophil count in the blood will be evaluated as part of the hematology assessment at all visits with the exception of Visits 6 (Day 56), 7 (Day 70), and 9 (Day 118) as indicated in the Schedule of Events (Appendix A). This assessment will be evaluated centrally.

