8.0 STATISTICAL ANALYSIS

This is an open-label study. Thus, only descriptive statistics are planned. All data collected on the case report forms (CRFs) will be summarized for the clinical study report (CSR).

All continuous parameters will be summarized using standard summary statistics as appropriate (n, mean, standard deviation, median, minimum, maximum, 25th percentile, and 75th percentile).

Summary statistics for categorical variables will include frequency counts and percentages. Summaries will be presented for all patients and by Treatment Phase and Follow-up Evaluation.

Details will be specified in the statistical analysis plan.

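### Apart from blood eosinophils, SAP 9.3.2 plans only by-subject category listings for haematology and biochemistry, short of the summaries that protocol 8.0 promises

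*SAP*

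**What the plan says.** Protocol 2.2 lists "Laboratory evaluation (hematology, biochemistry, anti-bertilimumab antibodies") under the primary safety endpoints. Protocol 8.0 states that "All continuous parameters will be summarized using standard summary statistics as appropriate", and leaves the details to the SAP.

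SAP 7.1.2 places laboratory evaluation among the additional safety endpoints. Under Hematology / Chemistry, SAP 9.3.2 defines five categories (clinically significant or not, below or above range, and normal) and plans two outputs:

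- A "By-test and by-subject listing of Hematology/ Chemistry results across visits". A note adds: "The results will be presented using the above categories, where CS results will be highlighted". Screening values are left out because local laboratories produced them.
- A "By-subject listing of clinically significant abnormal hematology / urinalysis results".

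SAP 9 opens with a general convention: "Numerical variables will be tabulated using mean, standard deviation, minimum, median, maximum and number of observations".

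One haematology analyte is treated separately. Protocol 5.6.2 says "Eosinophil count in the blood will be evaluated as part of the hematology assessment". SAP 7.4 makes the absolute count a pharmacodynamic endpoint, by visit and as change from baseline, and SAP 9.6 gives it descriptive statistics and mean plots.

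**The concern.** The primary objective is safety. Repeated central-laboratory values are the main numerical safety data from this repeat-dose study, and a paired change from pre-dose is the natural way to look for a consistent movement in a small group. A programmer who follows the laboratory bullets as written would produce no such summary. A mean rise in creatinine or a fall in platelets that left most patients within range would appear in no named table.

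The adverse event tables would not make up for this. Under protocol 5.3.7 and 7.1 a laboratory finding becomes an adverse event when it is clinically important, is associated with signs or symptoms, or leads to withdrawal. A drift within the normal range need not meet any of these.

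**Working it through.** **1. Planned outputs side by side (SAP 9.2, 9.3.2, 9.6)**

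| Data | Summary by visit | Change or shift | Category frequencies |
|---|---|---|---|
| Vital signs | yes | change | – |
| ECG | yes | change from Screening | yes |
| Anti-bertilimumab antibodies | yes | change from Visit 2 | – |
| Weight | yes | – | – |
| Physical examination | – | shift table | yes |
| Screening serology (same five categories) | – | – | yes |
| Blood eosinophils (PD) | yes | change from baseline | – |
| All other haematology, all biochemistry | none named | none named | none named |

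Two rows are telling. Anti-bertilimumab antibodies share the protocol's laboratory endpoint line with haematology and biochemistry, yet only the antibodies are summarised. Screening serology uses the identical five categories and then adds a frequency distribution, a sentence that the haematology and chemistry text lacks.

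Protocol 5.3.7 names 13 biochemistry tests. None has a named summary, change or shift table. The same holds for haemoglobin, platelets and every other haematology analyte except eosinophils.

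**2. What a category display can show (illustration)**

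The documents give no analyte variances and no sample-size or precision calculation, so there is no figure of the plan's own to reproduce. Assume a normally distributed analyte, a reference range of mean ±1.96 SD, patients centred on that range with the same SD, and the same upward shift s (in SD) in every patient.

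P(normal) = Φ(1.96 − s) − Φ(−1.96 − s); P(above range) = 1 − Φ(1.96 − s).

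| Shift s | P(normal) | Expected above range, of 15 |
|---|---|---|
| 0 | 0.950 | 0.37 |
| 0.25 | 0.943 | 0.65 |
| 0.5 | 0.921 | 1.08 |
| 1.0 | 0.830 | 2.53 |

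At s = 1.0 the expected number in the normal category falls only from 0.950 × 15 = 14.25 to 0.830 × 15 = 12.45.

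**3. What a change summary can show**

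With within-patient correlation r and equal SD at both visits, SD of change = √(2(1 − r)). The 95% half-width is t(0.975, 14) × SD / √15, with t = 2.145.

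- r = 0.5: SD 1.000, half-width 0.55
- r = 0.7: SD 0.775, half-width 0.43
- r = 0.8: SD 0.632, half-width 0.35

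A 1 SD mean change stands clear of zero throughout. A 0.5 SD change is borderline: 0.07 to 0.93 at r = 0.7, but −0.05 to 1.05 at r = 0.5. If only 10 patients contribute and the SD of change is 1.0, a 1 SD change has the interval 0.28 to 1.72 and a 0.5 SD change has −0.22 to 1.22.

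**4. Multiplicity**

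The 13 biochemistry tests at four post-baseline visits give 13 × 4 = 52 mean changes. With no true change, about 0.05 × 52 = 2.6 nominal 95% intervals would exclude zero by chance.

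**The case against.** The strongest reply is that the general convention at the head of SAP 9 already covers laboratory values. It sits above 9.3.2 and excludes nothing, so the table may simply not be itemised. That is a possible reading, and the SAP does not forbid the summary. But vital signs, ECG and antibodies each restate that they will be summarised despite the same convention, while the laboratory bullets specify listings. The convention does not clearly override them.

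Second, the listing may show numerical values flagged by category, and not categories alone. SAP 10 also promises listings of all data available from the CRF, although the documents do not say whether central-laboratory values are held there. With up to 15 patients, a consistent movement could then be read by eye. This stands in part: it is not established that the plan hides such a movement. A listing is still not the summary that protocol 8.0 describes.

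Third, clinically important abnormalities are reported and tabulated as adverse events. This is correct and limits the consequence to changes below that threshold.

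Two stronger readings are tempting. A reader might infer that no haematology result is ever tabulated; the eosinophil summaries in SAP 7.4 and 9.6 contradict this. A reader might also call an in-range shift drug-related. The design does not allow that: there is one arm, patients take oral corticosteroids on a recommended weekly taper (protocol 6.8.1), and rescue therapy is permitted (6.8.2). A mean change could reflect steroid dose or disease course.

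**Conclusion.** The point holds with its limits stated. For all 13 biochemistry tests and every haematology analyte except eosinophils, SAP 9.3.2 names only by-subject listings. This falls short of protocol 8.0 for tests that protocol 2.2 counts among the primary safety endpoints. The qualifier in protocol 8.0 that statistics are used as appropriate does not explain why these tests differ from vital signs or antibodies.

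The size is illustrative and rests on the assumptions above: a ±1.96 SD reference range, a uniform shift, correlations of 0.5 to 0.8 and 15 contributing patients. A 1 SD shift would leave 83% of values normal yet be plain in a change table. A 0.5 SD shift would leave 92% normal and be visible only at the higher correlations. Any such finding would be a descriptive signal for follow-up, not an estimate of drug effect.

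**What to change.** In SAP 9.3.2, under Hematology / Chemistry:

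- For each centrally measured analyte, add descriptive statistics by visit of the value, and of the change from Visit 2 pre-dose at Visits 3, 4, 5 and 8. Visit 2 is the usable baseline because screening values are local and are not presented. Convert the US and Israeli central-laboratory results to common units first.
- Optionally add a category shift table from Visit 2 to Visits 4, 5 and 8. It would show movement out of range but cannot show a shift within it, so it does not replace the change summary. It would also differ from the physical examination output, a "Shift table of normal/abnormal non-clinically significant (NCS)/abnormal clinically significant (CS) transitions from Screening to Visit 4" and Visit 8.
- Correct the second listing to cover haematology and chemistry. The laboratory panel in protocol 5.3.7 contains no urinalysis, and as written clinically significant chemistry has no dedicated listing.
- State that the changes are read descriptively, because with this many analytes and visits some will look notable by chance.

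The cost is a few table shells. No new data are needed.
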